## Appendix B: Maintenance Phase

When sufficient data have been collected to adequately evaluate all study endpoints, and after treatment assignment has been unblinded, the Sponsor may initiate a Maintenance Phase. Upon initiation of the Maintenance Phase, the Sponsor considers the safety and efficacy profile of the experimental treatment regimen within this study to have been sufficiently established for regulatory purposes. The Sponsor is to notify the sites if or when the study will enter the Maintenance Phase or if an alternative post-Study Completion option will be implemented ([Section 6.3](#)).

In the Maintenance Phase subjects will continue to receive active study treatment until a criterion for protocol-defined discontinuation has been met ([Section 3.6.1](#)). Subjects in the Maintenance Phase are to undergo periodic safety assessments (including local laboratory tests) and tumor assessments; the nature and frequency of these assessments are to be performed per institutional standard of care and guidance from the Sponsor as necessary. It is the Investigator's responsibility to ensure that subject visits occur frequently enough and adequate assessments are performed to ensure subject safety.

In order to continue to collect important safety information on subjects still enrolled in the study, reporting of SAEs, AESIs, and other reportable events (pregnancy, DILI and medication errors with sequelae) is to continue per protocol ([Section 8.2](#)).

Further, the following events (whether serious or not) are to be reported using the same process as for reporting SAEs described in protocol [Section 8.2](#) (though SAE reporting timeline requirements do not apply to non-serious events reported in these categories):

- Adverse events of special interest (AESIs)
- Adverse events, whether serious or not, leading to study treatment discontinuation
- Adverse events, whether serious or not, leading to study treatment dose modification (ie, causing study treatment to be interrupted, delayed, or reduced)

Subjects who discontinue study treatment in the Maintenance Phase, or who had previously discontinued study treatment but had not yet completed the Post-Treatment Follow-Up Visits (ie, FU-1 and FU-2) at the time the transition to the Maintenance Phase, will undergo the final safety assessment at the Post-Treatment Follow-up Visits. Upon initiation of the Maintenance Phase, no further follow up is required for any subject who has completed the FU-1 and FU-2 Visits.

CONFIDENTIAL

Protocol XL184-313 Protocol Amendment 3.0  
Page 156 of 193

Study drug accountability is to continue as described in [Section 6.5](#).

See the Maintenance Phase Schedule of Assessments below. To receive study treatment supplies it may be necessary for subjects to visit the study site more frequently than clinic visits for safety and tumor evaluations performed per standard of care.

Site monitoring visits will occur at a reduced frequency but must be frequent enough to ensure adherence to GCP, protocol compliance, adequate subject safety follow-up, study drug accountability, and reporting of SAEs and other reportable events.

During the Maintenance Phase no data are to be entered into CRFs. Study central laboratory samples are not to be obtained. Local laboratory results are not to be submitted to the study local laboratory management vendor, radiographic images to the study central imaging vendor, or ECGs to the study central ECG vendor.

CONFIDENTIAL

Protocol XL184-313 Protocol Amendment 3.0  
Page 157 of 193

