- Significant noncompliance with the protocol schedule in the opinion of the Investigator or the Sponsor.
- Subject is determined to have been randomized to receive placebo following study-wide unblinding

In addition, specific criteria for discontinuation of cabozantinib are provided in [Section 6.6.2](#) and for discontinuation of nivolumab/ipilimumab are provided in [Section 6.6.3.2](#). The maximum treatment period for nivolumab/ipilimumab is specified in [Section 3.4](#).

To ensure timely Sponsor notification of study treatment discontinuations, site personnel are to promptly record treatment discontinuations in the study IRT. The reason for study treatment discontinuation must be recorded in source documents and CRFs. If a subject fails to return for the protocol-defined visits, an effort must be made to determine the reason. If the subject cannot be reached by telephone, at the minimum a registered letter requesting contact with the clinic should be sent to the subject (or the subject's legal guardian).

For subjects who discontinue study treatment, every effort must be made to undertake protocol-specified follow up procedures including end of treatment assessments, survival

CONFIDENTIAL

Protocol XL184-313 Protocol Amendment 3.0  
Page 54 of 193

follow-up, and documentation of subsequent anti-cancer treatment(s) unless consent for non-interventional study assessments is also withdrawn.

If a subject is discontinued from study treatment because of an AE (including AESI; [Table 8-1](#)) considered to be related to study treatment, the event must be followed until resolution or determination by the Investigator that the event has become stable or irreversible.

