Subjects with QTc prolongation and symptoms must be monitored closely until the QTc elevation and symptoms have resolved. Cabozantinib treatment may be restarted but only at a reduced dose level if all of the following conditions are met:

CONFIDENTIAL

Protocol XL184-313 Protocol Amendment 3.0  
Page 101 of 193

- Symptoms are determined to be unrelated to the QT interval prolongation
- The QTcF value  $> 500$  ms or increase of  $> 60$  ms above baseline is not confirmed by a **cardiologist consultation**.
- Cabozantinib treatment has been interrupted through a minimum of 1 week following the return of the QTcF to  $\leq 500$  ms and  $\leq 60$  ms above baseline
- Sponsor has reviewed all available information and has agreed to the continuation of study treatment.

Following reinitiation of study treatment, ECGs must be repeated weekly for 2 weeks, then every 2 weeks for 1 month, then according to the protocol-defined time points.

Cabozantinib treatment must be permanently discontinued if either of the following applies:

- Cardiac evaluation confirms that symptoms are the consequence of QT interval prolongation
- Recurrence of QTcF prolongation (confirmed by central ECG lab) after reinitiation of study treatment at a reduced dose

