### **8.3 Adverse Events of Special Interest**

Adverse events of special interest (AESIs) consist of immune-mediated AEs associated with ICIs, cases of potential DILI, and suspected transmission of an infectious agent by the study treatment ([Table 8-1](#)).

AESIs will be reported to the Sponsor or designee using the SAE reporting form irrespective of whether the event is serious or nonserious; all AESIs must be reported within 24 hours using the SAE process as described in [Section 8.2](#).

Guidance for management of immune-mediated AEs is provided in the protocol ([Section 6.6.3](#)) and can also be found in the local prescribing information for nivolumab and ipilimumab.

CONFIDENTIAL

Protocol XL184-313 Protocol Amendment 3.0  
Page 121 of 193

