#### **8.4 Follow-Up of Adverse Events**

Nonserious AEs (see below for AESIs [[Table 8-1](#)]) are to be recorded in the CRF until 30 days after the date of the decision to discontinue study treatment (the later of the date of the decision by the Investigator to permanently discontinue study treatment or the date of the last dose of study treatment taken by the subject). The status of unrelated SAEs that are ongoing after the date of the decision to discontinue study treatment will be documented until the 100-day FU-2 visit.

All AESIs (regardless of seriousness) and all related SAEs that are ongoing 100 days after the date of the decision to discontinue study treatment (the later of the date of the decision by the Investigator to permanently discontinue study treatment or the date of the last dose of study treatment taken by the subject), and AEs assessed as related that led to study treatment discontinuation that are ongoing 100 days after the date of the decision to discontinue study treatment, are to be followed until either:

- the AE has resolved
- the AE has improved to Grade 2 or lower
- The investigator determines that the event has become stable or irreversible.

Further details on follow-up procedures are provided in [Appendix H](#).

CONFIDENTIAL

Protocol XL184-313 Protocol Amendment 3.0  
Page 123 of 193

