- All SAEs that are judged by the Investigator to be related to study treatment that start or worsen at any time after the subject’s initial informed consent are to have a Drug Safety SAE Form completed. Such events that occur prior to the FU-2 visit are to be entered into the EDC. Such events continuing at the FU-2 visit are to be followed until resolution (as defined above), with evidence of resolution provided on updates to the Drug Safety SAE Form. In the EDC, only documentation of the status of “ongoing” at the FU-2 visit is required.

CONFIDENTIAL

A summary of the event surveillance (Table H-1) and follow-up requirements (Table H-2) are shown in the following page:

CONFIDENTIAL

Protocol XL184-313 Protocol Amendment 3.0  
Page 184 of 193

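### In the Maintenance Phase, Appendix B conflicts with safety rules elsewhere in the protocol on event follow-up after FU-2, reporting time for non-serious AESIs, and central ECG confirmation

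*Protocol*

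**What the plan says.** **Follow-up.** Appendix B states that subjects who stop treatment in the Maintenance Phase, or who stopped earlier but have not finished FU-1 and FU-2, "will undergo the final safety assessment at the Post-Treatment Follow-up Visits". It then adds that "no further follow up is required for any subject who has completed the FU-1 and FU-2 Visits". Section 8.4 takes "All AESIs (regardless of seriousness) and all related SAEs that are ongoing 100 days after the date of the decision to discontinue study treatment", together with related AEs that led to discontinuation, and has them followed until they resolve, improve to Grade 2 or lower, or are judged stable or irreversible. Section 3.6.1 says of related AEs that led to discontinuation that "the event must be followed until resolution or determination by the Investigator that the event has become stable or irreversible". Appendix H says of related SAEs, and in the same terms of AESIs: "Such events continuing at the FU-2 visit are to be followed until resolution (as defined above), with evidence of resolution provided on updates".

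**AESI reporting time.** Section 8.3 requires that "all AESIs must be reported within 24 hours using the SAE process", whether or not the event is serious. Section 5.5 and the text of Appendix B first continue SAE, AESI and DILI reporting under Section 8.2. They then list three categories, AESIs first, and say that "SAE reporting timeline requirements do not apply to non-serious events reported in these categories". The Appendix B schedule table divides the events differently. One row sends SAEs, AESIs and DILI to Section 8.2 with no relaxation. The next row relaxes the time only for AEs, including AESIs, that lead to discontinuation or dose modification.

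**ECGs.** Appendix B, in its text and in the note under its table, says that ECGs are not to go to the central ECG vendor. Section 6.6.2.1.15 lists a central read among the actions that must follow an averaged QTcF finding at any time on study. It also gives two criteria for permanent discontinuation of cabozantinib, one of which is "Recurrence of QTcF prolongation (confirmed by central ECG lab) after reinitiation of study treatment at a reduced dose".

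**The concern.** Subjects in the Maintenance Phase are still in the trial, because Section 3.6.4 counts Maintenance Phase assessments towards the end of trial. A site therefore has two sets of instructions for the same patient. One site may close an unresolved AESI at FU-2 and another may follow it. One may report a non-serious AESI within 24 hours and another with no set time. Either course could be recorded as a deviation from some passage. Appendix B also ends CRF entry in this phase, so safety reports become the main route by which such events reach the sponsor, and the rules for them need to be unambiguous. At stake is the consistency of safety follow-up, not any efficacy result.

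**Working it through.** There is no stated figure to reproduce. The check sets the passages side by side and then bounds the number of subjects.

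**1. Do both sets of rules apply?** Appendix B continues treatment until a Section 3.6.1 criterion is met, and Section 3.6.1 refers to Section 6.6.2 for the cabozantinib criteria. Sections 3.6.1, 6.6.2.1.15, 8.3 and 8.4 and Appendix H contain no Maintenance Phase exception for these points. No clause says that Appendix B overrides them. The synopsis and Section 3.3 do say that reporting continues under requirements specific to the Maintenance Phase, but that wording covers reporting only, not follow-up or ECG reads.

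**2. Follow-up after FU-2, by type of event.**
- *Related SAEs:* Section 8.2.1, which Appendix B keeps in force through Section 8.2, makes them reportable beyond 100 days and asks the investigator to keep monitoring and reporting the outcome of SAEs. They remain covered despite the Appendix B sentence.
- *AESIs:* Section 8.4 and Appendix H require follow-up to an endpoint, whereas Appendix B requires none. For non-serious AESIs, Section 8.2.1 does not fill the gap.
- *Non-serious related AEs that led to discontinuation:* Sections 3.6.1 and 8.4 and Appendix H require follow-up, whereas Appendix B requires none. Table H-2 places the evidence of resolution in source documents only.

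**3. Reporting time for AESIs.**
- *Serious AESIs:* 24 hours under every passage, so there is no conflict.
- *Non-serious, leading to discontinuation or dose modification:* exempt under Section 5.5, the Appendix B text and the second table row. Section 8.3 requires 24 hours.
- *Other non-serious AESIs:* exempt under Section 5.5 and the Appendix B text, but not under the first table row or Section 8.3.
- *Non-serious potential DILI:* an AESI in Table 8-1, so exempt under the text, yet also named separately for Section 8.2 reporting with no relaxation. Section 6.6.1 requires all study drugs to stop for a drug-related case with the stated enzyme and bilirubin elevations, so such a case also fits the relaxed second row. It falls under both rules.

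**4. QTcF.** The recurrence criterion needs confirmation by the central ECG laboratory. If no ECG may be sent there, it cannot be met. The initial detection of prolongation, the interruption and the notice to the Sponsor run on the site's own read and are unaffected. So is the other permanent-stop criterion, which rests on cardiac evaluation.

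**5. Number of subjects.** Inputs are 840 randomized and 433 deaths at the final OS analysis, expected at about month 69 (Protocol 9.5).
- Alive at that point: 840 − 433 = 407 at most.
- Assume that 1% to 5% have an unresolved AESI or related event past FU-2 at the switch. The documents give no such rate.
- 0.01 × 407 = 4.07 and 0.05 × 407 = 20.35, so about 4 to 20.
- This is a ceiling, because subjects still on treatment at the switch are not yet past FU-2.
- The study can also complete earlier. Non-rejection of PFS, planned at about month 23 with about 117 deaths, would leave 840 − 117 = 723 alive. The same assumption gives 7 to 36, a looser ceiling because more subjects would still be on treatment. Section 6.3 also lets the sponsor end drug access in that case.

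**6. Drugs still in use at month 69.** Accrual takes 21 months and nivolumab is given for at most 24, so planned nivolumab ends by about month 21 + 24 = 45, some 69 − 45 = 24 months earlier. Ipilimumab stops after four doses. Section 3.6.1 lists assignment to placebo, once known after study-wide unblinding, among the reasons for discontinuation. The exposure that remains is mainly cabozantinib.

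**The case against.** The strongest reply is that these are intended simplifications for an optional late phase.

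On reporting time, the exemption appears in both Section 5.5 and Appendix B, covers non-serious events only, and is backed by the reference to Maintenance-Phase-specific reporting. That largely answers the conflict between the text and Section 8.3. It does not answer the disagreement between the Appendix B text and its own table, or the double listing of DILI.

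On follow-up, the sentence can be read as ending only scheduled visits and survival contacts. Section 5.7.12 does drop survival contacts in this phase, and Appendix B asks for monitoring sufficient for adequate safety follow-up. But the sentence directly before it concerns the final safety assessment, and nothing confines it to survival. A site could reasonably take it to end safety follow-up.

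On QTcF, local reads, interruption, Sponsor notification, Sponsor agreement to restart, and discontinuation on the investigator's judgment under Section 3.6.1 all continue. Section 6.6.2.1.15 also reports no subject above 500 ms in the 140 mg study. This stands as an argument about impact. It does not make the criterion reachable.

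A reader might infer more: that sites may drop related SAEs, that every AESI loses its 24-hour limit, that all 840 subjects are exposed, that affected patients are on or just off all three drugs, or that QTc protection has gone. The documents do not support these readings. Section 8.2 covers related SAEs, serious AESIs keep the 24-hour limit, 433 deaths define month 69, planned nivolumab ends about two years before it, and the local QTc steps remain.

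**Conclusion.** The conflicts are real and no precedence clause settles them, but they are narrow. (1) Follow-up of ongoing events after FU-2 is contradictory, mainly for AESIs and for non-serious related AEs that led to discontinuation. (2) For non-serious AESIs, the Appendix B text and table disagree on which are exempt from the SAE timeline, Section 8.3 exempts none, and a non-serious potential DILI case falls under both rules. (3) One of two permanent-discontinuation criteria for QTcF cannot be met as written. It matters only for a subject who had prolongation, restarted at a reduced dose and then recurred.

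The ceiling of about 4 to 20 subjects rests on final OS timing and an assumed 1–5% rate. The contradictions themselves do not depend on that rate. No efficacy analysis is affected, since only data collected before the phase enter the clinical study report. The point is worth correcting because it bears on safety and is cheap to settle.

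**What to change.** Reconcile Appendix B (text and table) and Section 5.5 with Sections 3.6.1, 8.3, 8.4 and 6.6.2.1.15 and Appendix H, so that a site finds one rule for each of three points:
- whether and until when AESIs, related SAEs and related AEs that led to discontinuation are followed if ongoing at FU-2;
- the reporting time for each class of non-serious AESI, with potential DILI placed once;
- how the central-read action and the recurrence criterion for QTcF operate in this phase.

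Also state which section governs if passages still differ. Which rule applies is a clinical decision for the sponsor, and none is proposed here.

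The cost is a few sentences and a table edit at the next amendment. Depending on the sponsor's choice, some safety contacts or ECG handling may need to be retained. Sample size, alpha and the planned analyses do not change.

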## Schedule of Assessments: Maintenance Phase

Assessment	Study Period / Visit	
	While Subject is Receiving Study Treatment (Until Treatment is Permanently Discontinued)	Post-Treatment Follow-Up Visits (ie, FU-1 and FU-2)
Study drug accountability	Every time study drug is dispensed	✓ a
Study treatment	Nivolumab infusion: Once every 4 weeks (maximum of 2 years of treatment in total); Cabozantinib (oral): Daily. Study treatment may continue until a criterion for discontinuation is met (Section 3.6.1).	-
Safety evaluation: Clinical examination and local laboratory assessments per SOC	Frequency per standard of care	✓ a
Reporting of SAEs, AESIs, and other reportable events (DILI, pregnancy, medication errors with sequelae)	Submit reports to Sponsor per Section 8.2	
Reporting of AEs (including AESIs): 
 
• leading to study treatment discontinuation
 
• leading to study treatment dose modification (ie, causing study treatment to be withheld or reduced)
 
	Submit reports to Sponsor per the same process as for reporting SAEs per Section 8.2 SAE reporting timeline requirements do not apply to non-serious events reported in these categories	
Tumor assessments: Imaging methods per SOC	Frequency per standard of care	-

AE, adverse event; DILI, drug-induced liver injury; FU-1, 30-Day Post-Treatment Follow-up Visit; FU-2, 100-Day Post-Treatment Follow-up Visit; SAE, serious adverse event; SOC, standard of care

No data will be entered into electronic case report forms. Do not submit local laboratory results to the study local laboratory management vendor, radiographic images to the study central imaging vendor, or ECGs to the study central ECG vendor.

a Subjects should return all unused study medication and undergo a safety evaluation per standard of care.

CONFIDENTIAL

Protocol XL184-313 Protocol Amendment 3.0  
Page 158 of 193

## Appendix C: Karnofsky Performance Status Criteria

ECOG Performance Status Scale (reference only)		Karnofsky Performance Status Scale	
Grade	Description	Percent	Description
0	Normal activity. Fully active, able to carry on all pre-disease performance without restriction.	100	Normal, no complaints, no evidence of disease.
		90	Able to carry on normal activity; minor signs or symptoms of disease.
1	Symptoms, but ambulatory. Restricted in physically strenuous activity, but ambulatory and able to carry out work of a light or sedentary nature (eg, light housework, office work).	80	Normal activity with effort; some signs or symptoms of disease.
		70	Cares for self, unable to carry on normal activity or to do active work.
2	In bed < 50% of the time. Ambulatory and capable of all self-care, but unable to carry out any work activities. Up and about more than 50% of waking hours.	60	Requires occasional assistance, but is able to care for most of his/her needs.
		50	Requires considerable assistance and frequent medical care.
3	In bed > 50% of the time. Capable of only limited self-care, confined to bed or chair more than 50% of waking hours.	40	Disabled, requires special care and assistance.
		30	Severely disabled, hospitalization indicated. Death not imminent.
4	100% bedridden. Completely disabled. Cannot carry on any self-care. Totally confined to bed or chair.	20	Very sick, hospitalization indicated. Death not imminent.
		10	Moribund, fatal processes progressing rapidly.
5	Dead.	0	Dead.

CONFIDENTIAL

Protocol XL184-313 Protocol Amendment 3.0  
Page 159 of 193

## **Appendix D: Highly Effective Methods of Contraception**

In Inclusion Criterion #10 (Section 4.2), sexually active fertile subjects and their partners must agree to use highly effective methods of contraception that alone or in combination result in a failure rate of less than 1% per year when used consistently and correctly during the course of the study and until the end of relevant systemic exposure, defined as 5 months for women, and 7 months for men, after the last dose of study treatment.

The effect of cabozantinib on the PK of contraceptive steroids has not been investigated. Because oral contraceptives might possibly not be considered as “effective methods of contraception,” they should be used together with another method.

